#### 8.1 Adverse Events

Adverse event terms recorded on the CRF will be mapped to preferred terms and system organ class using the Medical Dictionary for Regulatory Activities (MedDRA). The severity of AEs will be measured by CTCAE (Cancer Therapy Evaluation Program 2009) version 4 guidelines. The investigator will judge each event to be "not related" or "related" to study treatment.

A TEAE is defined as any event with an onset date on or after the date of the first dose of study drug or any ongoing event on the date of the first dose of study drug that worsens in severity after the date of the first dose of study drug.

Only TEAEs with an onset date through the end of the safety observation period (see section 4.5) will be tabulated in summary tables.

For the purpose of calculating treatment emergence and inclusion in summary tables, incomplete onset dates will be imputed as detailed in Appendix A.

For AE reporting, percentages  $\geq 10\%$  will generally be presented as integers, those  $\leq 10\%$ 

will be presented with 1 decimal place (e.g. X.X%). Rounding rules are provided in Appendix B. The calculations of percentages will be based on original unrounded values.

An overall summary of adverse events will be provided with the number and percent of subjects who experienced the following types of events during the safety observation period (unless otherwise noted) in each treatment arm:

- Subjects with a TEAE
- Subjects with a Related TEAE
- Subjects with a Serious TEAE
- Subjects with a Serious Related TEAE at any time
- Subjects with a Worst-Grade 3 or 4 TEAE
- Subjects with a Worst-Grade 3 or 4 Related TEAE
- Subjects with a Worst-Grade 4 TEAE
- Subjects with a Worst-Grade 4 Related TEAE
- Subjects with a Grade 5 TEAE at any time
- Subjects with a Grade 5 TEAE
- Subjects with a Grade 5 TEAE through 30 days after the last dose of the study treatment
- Subjects with a Grade 5 AE judged not to be causally related to PD through 30 days of last dose of the study treatment
- Subjects with a Grade 5 AE >30 days after the last dose of the study treatment
- Subjects with a Grade 5 AE judged not to be causally related to PD >30 days of last dose of the study treatment
- Subjects with a Related Grade 5 TEAE at any time
- Subjects with a Related Grade 5 TEAE
- All subjects who died
- Subjects who died within 30 days after date of last dose of study treatment
- Subjects with a TEAE leading to Dose Modification
- Subjects with a TEAE leading to Dose Reduction
- Subjects with a TEAE leading to Dose Hold
- Subjects with TEAE leading to Treatment Discontinuation
  - > TEAEs not related to disease progression
  - > TEAEs related to disease progression

The following summaries of AEs will be provided:

TEAE included	Row-levels (sorted by)	Columns				
S	ubject Incidence by SOC, Preferred Tern	and Severity				
All	SOC and PT	Worst severity:				
	(MedDRA standard)	All Grades, Grade 3/4, Grade 4, Grade 5				
Related	SOC and PT	Worst severity:				
	(MedDRA standard)	All Grades, Grade 3/4, Grade 4, Grade 5				
Serious	SOC and PT	Worst severity:				
	(MedDRA standard)	All Grades, Grade 3/4, Grade 4, Grade 5				
Related Serious	SOC and PT	Worst severity:				
	(MedDRA standard)	All Grades, Grade 3/4, Grade 4, Grade 5				
Subject Incidence by Preferred Term and Severity						
All	PT	Worst severity:				
	(descending frequency of Any Grade)	All Grades, Grade 3/4, Grade 4, Grade 5				
Related	PT	Worst severity:				
	(descending frequency of Any Grade)	All Grades, Grade 3/4, Grade 4, Grade 5				
Leading to dose reduction	PT	Worst severity:				
Landing Andreas Includ	(descending frequency of Any Grade)	All Grades, Grade 3/4, Grade 4, Grade 5				
Leading to dose hold	PT (descending frequency of Any Crade)	Worst severity:				
Leading to dose modification	(descending frequency of Any Grade) PT	All Grades, Grade 3/4, Grade 4, Grade 5 Worst severity:				
Leading to dose modification	(descending frequency of Any Grade)	All Grades, Grade 3/4, Grade 4, Grade 5				
Not Related to Disease	PT	Worst severity:				
Progression and Leading to	(descending frequency of Any Grade)	All Grades, Grade 3/4, Grade 4, Grade 5				
Study Treatment Discontinuation	(22220	2.200, 3.000 5, 3.000 1, 3.000 0				
Related to Disease Progression	PT	Worst severity:				
and Leading to Study Treatment	(descending frequency of Any Grade)	All Grades, Grade 3/4, Grade 4, Grade 5				
Discontinuation						
All	PT	Worst severity:				
	(descending frequency of Grade 3/4)	All Grades, Grade 3/4, Grade 4, Grade 5				
Related	PT	Worst severity:				
	(descending frequency of Grade 3/4)	All Grades, Grade 3/4, Grade 4, Grade 5				
Leading to dose reduction	PT (C. L.O.)	Worst severity:				
Loading to door hold	(descending frequency of Grade 3/4)	All Grades, Grade 3/4, Grade 4, Grade 5				
Leading to dose hold	(descending frequency of Grade 3/4)	Worst severity: All Grades, Grade 3/4, Grade 4, Grade 5				

Macrovascular Invasion per	(descending frequency of Gr3/4 in the	All Grades, Grade 3/4, Grade 4, Grade 5
Cancer History CRF	cabo arm)	
All SAEs for Subjects without	PT	Worst severity:
Macrovascular Invasion per	(descending frequency of Gr3/4 in the	All Grades, Grade 3/4, Grade 4, Grade 5
Cancer History CRF	cabo arm)	

The following data listings will also be provided with indicators for grade, relationship, seriousness, dose day of the event start/stop, days since last dose, action taken with study treatment:

- All AEs
- Grade 5 AEs
- Serious AEs other than death

# 8.2 Deaths

All reported subject deaths and whether death was causally associated with the disease under study (HCC) will be summarized by treatment arm for all subjects in the Safety population. The primary cause of death recorded on the CRF will be mapped to preferred term and system organ class using MedDRA. The coded terms will be merged with AE records to determine the relationship to study treatment.

Deaths will be summarized in 2 main categories as follows:

- Deaths within 30 days after the date of receipt of the last dose of study treatment
- Deaths greater than 30 days after the date of receipt of last dose of study treatment

Summary of primary cause of death will be tabulated under each category by causality to study disease and relationship to study drug.

All reported subject deaths will be listed.

# 8.3 Laboratory Assessments

## 8.3.1 Variables

The following treatment-emergent laboratory abnormalities will be summarized. A treatment emergent laboratory abnormality is defined as any laboratory abnormality with an onset date on or after the date of the first dose of study drug.

		SDTM	Grading
Category	Abnormality	LBTESTCD	System
•	WBC increased		
Hematology	WBC decreased	WBC	CTCAE
	ANC decreased	NEUT	CTCAE
	Lymphocytes increased		
	Lymphocytes decreased	LYM	CTCAE
	Platelets decreased	PLAT	CTCAE
	Hemoglobin increased		
	Hemoglobin decreased	HGB	CTCAE
Serum chemistry	Albumin decreased	ALB	CTCAE
	ALP increased	ALP	CTCAE
	Amylase increased	AMYLASE	CTCAE
	ALT increased	ALT	CTCAE
	AST increased	AST	CTCAE
	Calcium, corr increased	CACORR	
	Calcium, corr decreased		CTCAE
	Calcium, ion increased		
	Calcium, ion decreased	CAION	CTCAE
	Creatinine increased	CREAT	CTCAE
	GGT increased	GGT	CTCAE
	Glucose increased		
	Glucose decreased	GLUC	CTCAE
	LDH increased	LDH	Sponsor
	Lipase increased	LIPASE	CTCAE
	Magnesium increased		
	Magnesium decreased	MG	CTCAE
	Phosphate decrease	PHOS	CTCAE
	Potassium increased		
	Potassium decreased	K	CTCAE
	Sodium increased		
	Sodium decreased	NA	CTCAE
	Total bilirubin increased	BILI	CTCAE
·	Uric acid increased 	CYURIAC	CTCAE
Urine chemistry	UPCR increased	PROTCRT	Sponsor
	Thyroid Stimulating Hormone increased		
Endocrinology 	Thyroid Stimulating Hormone decreased	TSH	HLN

<sup>1 TSH is held in the SDTM "chemistry" laboratory category; will use HLN = high, low, normal classification based on normal range

Sponsor-defined grades are to be applied to the following analytes:

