#### **3.2 Estimated Study Dates and Duration of Subject Participation**

It is estimated that it will take 25 months to randomize approximately 760 subjects at up to 200 global sites. The number of events required for the primary analysis of OS is expected to be observed approximately 38 months after the first subject is randomized. It is estimated that subjects will participate for an average of 3 to 5 months on study treatment. Subjects will be followed until death (median of 8 to 12 months) or Sponsor decision to no longer collect these data.

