**Table 5-1: Laboratory Panels**

Central Laboratory		
If performed by local laboratory in lieu of central lab assessment, submit results to study local laboratory management vendor		

Hematology
 
 
• White blood cell count (WBC) with differential (neutrophils [absolute neutrophil count; ANC], basophils, eosinophils, lymphocytes, monocytes)
 
• hematocrit
 
• platelet count
 
• red blood cell count
 
• hemoglobin
 
• reticulocytes
 
 
Coagulation
 
 
• Prothrombin time/international normalized ratio (PT/INR)
 
• Partial thromboplastin time (PTT)
 
 
Other Parameters
 
 
• Alpha-fetoprotein (AFP)b
 
	
Serum chemistry
 
 
• albumin
 
• total alkaline phosphatase
 
• amylase
 
• alanine aminotransferase (ALT)
 
• aspartate aminotransferase (AST)
 
• blood urea nitrogen (BUN)
 
• calcium (corrected)
 
• bicarbonate
 
• chloride
 
• creatinine
 
• <math>\gamma</math>-glutamyltranspeptidase (GGT)
 
• glucose
 
• lactate dehydrogenase (LDH)
 
• lipase
 
• magnesium
 
• phosphorus
 
• potassium
 
• sodium
 
• total bilirubin
 
• conjugated bilirubin
 
• unconjugated bilirubin
 
• total protein
 
• hemoglobin A1c, glycosylated (HbA1c; screening)
 
	
Urine chemistry
 
 
• Protein (spot urine; fully quantitative)
 
• Creatinine (fully quantitative)
 
• Urine protein/creatinine ratio (UPCR; spot urine)a
 
 
Thyroid function
 
 
• Thyroid stimulating hormone (TSH)
 
• Free T4 (required at screening; after screening only if TSH is outside normal range)
 
 
Hepatitis Virus Statusb
 
 
• Hepatitis B surface antigen, Hepatitis B core antibody, Hepatitis C antibody
 

Local Laboratory		

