### **6.7.3 Hepatobiliary Disorders**

Elevations of ALT, AST, and total bilirubin have been observed during treatment with cabozantinib.

A subject who has ALT, AST, and total bilirubin  $\leq 3.0 \times \text{ULN}$  at baseline and who develops  $\geq$  Grade 3 elevated ALT, AST, or total bilirubin should have study treatment interrupted and the dose reduced as outlined in Tables Table 6-3 and Table 6-4.

Subjects on this study may enter the study with elevations of AST/ALT up to  $5 \times \text{ULN}$  at baseline. Elevations of aminotransferases when hepatic tumors are present may not require dose modifications if there are no progressive changes in the aminotransferases (less than a doubling) and if there are no progressive elevations in serum total bilirubin concentration or coagulation factors. Cabozantinib treatment should be interrupted when transaminase increases are accompanied by progressive elevations of total bilirubin, and/or elevations of coagulation tests (eg, International Normalized Ratio [INR]). More frequent monitoring of transaminases should be considered and study treatment should be held until the etiology of the abnormalities is determined and these abnormalities are corrected or stabilize at clinically acceptable levels. If hepatic toxicity resolves during a temporary hold and was deemed related to study treatment, then study treatment may be restarted at a reduced dose. Study treatment should be discontinued if hepatic dysfunction is not reversible despite temporary interruption of study treatment. Elevations  $> 3 \times \text{ULN}$  of ALT or AST concurrent with  $> 2 \times \text{ULN}$  total bilirubin without other explanation can indicate drug-induced liver injury and drug should be permanently discontinued.

If possible, hepatotoxic concomitant medications should be discontinued in subjects who develop increased values of ALT, AST, or total bilirubin.

Evaluation of subjects with elevated transaminases or total bilirubin should be individualized and guided by the presence of specific risk factors such as illnesses which affect liver function (eg, infectious and non-infectious causes of hepatitis, liver cirrhosis, thrombosis of portal or hepatic vein), concomitant hepatotoxic medication, alcohol consumption, and cancer related causes. AEs which are based on hepatic dysfunction should be managed according to locally accepted clinical practice, including monitoring of appropriate laboratory functions.

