#### **6.7.11 Hemorrhagic Events**

Hemorrhagic events have been reported with approved drugs that inhibit VEGF pathways as well as with cabozantinib. In order to mitigate risk of severe hemorrhage, subjects should be evaluated for potential bleeding risk factors prior to initiating study treatment and monitored for bleeding events with serial complete blood counts and physical examination while on study. Risk factors for hemorrhagic events may include (but may not be limited to) the following:

- Tumor of the lung with cavitory lesions or tumor lesions which invades, encases, or abuts major blood vessels. The anatomic location and characteristics of tumor as well as the medical history must be carefully reviewed in the selection of subjects for study treatment.
- Recent or concurrent radiation
- Active peptic ulcer disease, ulcerative colitis, and other inflammatory GI diseases
- Underlying medical conditions which affect normal hemostasis (eg, deficiencies in clotting factors and/or platelet function, or thrombocytopenia)
- Concomitant medication with anticoagulants or other drugs which affect normal hemostasis
- History of clinically significant hemoptysis

Discontinue study treatment in subjects who experience a severe bleeding complication.

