Physical exam (PE) + weight (Section 5.7.2)	≤ 7 d (with height)	X (prior to first dose; symptom-directed PE)	X	X	X	X	Every 4 wks (W13D1, W17D1 etc)	X	
Vital signs (Section 5.7.3)	≤ 7 d	X (prior to first dose)	X	X	X	X	Every 4 wks (W13D1, W17D1 etc)	X	
ECOG (Appendix D: ECOG Performance Scale)	≤ 7 d	X (prior to first dose)	X	X	X	X	Every 4 wks (W13D1, W17D1 etc)	X	
12-lead ECG with QTc (Section 5.7.4) c	≤ 7 d	X (prior to first dose) d	X	X		X		X	
Hematology by central lab (Section 5.7.5) e	≤ 7 d	X (prior to first dose) d	X	X	X	X	Every 4 wks (W13D1, W17D1 etc)	X	
Serum chemistry by central lab (Section 5.7.5) e	≤ 7 d	X (prior to first dose) d	X	X	X	X	Every 4 wks (W13D1, W17D1 etc)	X	
Coagulation panel by central lab (Section 5.7.5) e	≤ 7 d	X (prior to first dose) d	X	X	X	X	Every 4 wks (W13D1, W17D1 etc)	X	
UPCR by central lab (Section 5.7.5) e	≤ 7 d	X (prior to first dose) d	X	X	X	X	Every 4 wks (W13D1, W17D1 etc)	X	

	Pre-randomization	Post-randomization							
	Screening (before randomization) a	W1D1 (≤ 3d after randomization)	W3D1 (±3 d)	W5D1 (±3 d)	W7D1 (±3 d)	W9D1 (±3 d)	Beyond Week 9 (±5 d)	30-day Post-Treatment Follow-Up (+14 d)	Extended Follow-Up
Fasting serum glucose by local lab (only if HbA1c result is unavailable; Section 5.7.5)	≤ 28 d								
Urinalysis by local lab (Section 5.7.5) e	≤ 7 d					X	Every 8 wks (W17D1, W25D1 etc)	X	
Serum pregnancy test by local lab (Section 5.7.5) e	≤ 7 d	X (prior to first dose) d		X		X	Every 4 wks (W13D1, W17D1 etc)	X	
Thyroid function panel by central lab (Section 5.7.5) e	≤ 28 d	X (prior to first dose) d				X	Every 8 wks (W17D1, W25D1 etc)	X	
AFP by central lab (Section 5.7.7) e	≤ 28 d	AFP every 8 weeks (± 5 d) after randomization (W9D1, W17D1 etc). Assessments should continue regardless of whether study treatment is given, reduced, interrupted, or discontinued until the later of 8 weeks after radiographic progression per RECIST 1.1 as determined by the investigator or the date of the decision to permanently discontinue study treatment							

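### SAP 8.3.1 lists no coagulation test, so the plan does not commit to a graded, laboratory-based table of INR or PTT worsening

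*SAP*

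**What the plan says.** **Collection.** Protocol Table 5-1 puts "Prothrombin time/international normalized ratio (PT/INR" and "Partial thromboplastin time (PTT" in the central-laboratory coagulation panel. The Appendix A row "Coagulation panel by central lab (Section 5.7.5" schedules that panel at screening, Weeks 1, 3, 5, 7 and 9, every 4 weeks from Week 13, and at the 30-day post-treatment visit. The Week 1 draw may be skipped if the screening sample is recent enough.

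**Clinical role.** Protocol 6.7.3 calls for interruption when transaminase rises are "accompanied by progressive elevations of total bilirubin, and/or elevations of coagulation tests (eg, International Normalized Ratio [INR" (the protocol's bracketed example ends there). Protocol 6.7.11 includes in its risk factors for hemorrhage "Underlying medical conditions which affect normal hemostasis (eg, deficiencies in clotting factors and/or platelet function, or thrombocytopenia", but names neither INR nor PTT.

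**Analysis.** SAP 8.3.1 states "The following treatment-emergent laboratory abnormalities will be summarized", followed by a table that gives each analyte a grading system (CTCAE, sponsor-defined, or high/low/normal). No coagulation analyte appears. The table does include "Uric acid increased" and ionized calcium, neither of which is in Protocol Table 5-1; the panel has corrected calcium only.

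**Elsewhere in the SAP.** INR is named as a baseline characteristic in 5.3 and enters Child-Pugh category shifts (7.5.6) as one component. SAP 8.3.2 promises, in general terms, reference-range flags, by-visit descriptive statistics, and shift tables by CTCAE grade and by high/low/normal. Its graded incidence table is confined to selected tests. Protocol 9.7.2 likewise promises only selected tests.

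**The concern.** The plan collects two coagulation tests throughout treatment and uses one of them in its guidance on liver toxicity, but the one place where the SAP selects analytes for graded reporting leaves both out. The list also contains two analytes that the protocol panel does not include, which suggests that it was not reconciled with Table 5-1.

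What is at stake is how liver and bleeding safety is described. The safety report would show ALT, AST, bilirubin and albumin by worst grade, with no assured counterpart for INR. Worsening confined to a minority of subjects is best shown as a count of subjects by grade and arm, and the SAP does not promise that count for coagulation. No efficacy result or formal test is affected, since safety is descriptive.

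**Working it through.** The plan states no figure on this point, so the check is a comparison of sections.

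**1. List against panel.** Coagulation tests in Protocol Table 5-1: 2 (PT/INR, PTT). Coagulation rows in SAP 8.3.1: 0. Analytes in SAP 8.3.1 but absent from Table 5-1: 2 (uric acid, ionized calcium).

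**2. How much data is involved.** Protocol 3.2 states: "It is estimated that subjects will participate for an average of 3 to 5 months on study treatment". With a month of 30.4375 days (SAP section 4), 3 months is 3 × 30.4375 / 7 = 13.0 weeks and 5 months is 5 × 30.4375 / 7 = 21.7 weeks. Scheduled on-treatment draws are then W1, W3, W5, W7, W9 and W13 = 6, or 8 with W17 and W21. Screening and the 30-day visit are additional, and the W1 draw may be waived.

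**3. What each other route gives.**

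| Route | What it gives for INR | What is missing |
|---|---|---|
| By-visit statistics (SAP 8.3.2) | Mean, SD, median, quartiles, minimum, maximum | Count of subjects by grade; change from baseline excludes local results |
| High/low/normal shift (8.3.2) | Direction of shift, if INR is included | Severity; no analytes named |
| CTCAE-grade shift (8.3.2) | Graded shift, if INR is included | No analytes named; 8.3.1 assigns INR no grading system |
| AE tables (8.1) | Worst grade of reported events | Depends on the investigator reporting the result |
| Child-Pugh shift (7.5.6) | Change of category | INR is one of five components, assessed every 8 weeks |

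**4. Sensitivity of Child-Pugh.** Protocol Appendix E gives 1 point for INR below 1.8 and 2 points for 1.8 to 2.3; category A is 5 to 6 points. INR can rise from 1.0 to 1.7 with no change in points. A subject at 5 points whose INR alone rises to 2.3 moves to 6 and stays in category A.

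**5. Central and local results.** SAP 8.3.2 admits local results to the graded tables but not to change from baseline. Protocol 5.7.5 allows local testing when a result is needed quickly, for example to monitor an adverse event. Protocol 5.6 asks for a paired central sample at unscheduled visits, but the by-visit tables run by scheduled visit. Urgent INR results are thus poorly placed to appear in the change-from-baseline summaries.

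**6. What a by-visit table would show (assumed scenario, not from the documents).** Let a fraction p of subjects rise by 1.0 in INR and the rest not change. Mean change = p × 1.0, SD = √(p(1 − p)), and the number affected among the 507 planned cabozantinib subjects = 507p.

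- p = 2%: mean 0.02, SD 0.14, about 10 subjects
- p = 5%: mean 0.05, SD 0.22, about 25 subjects
- p = 10%: mean 0.10, SD 0.30, about 51 subjects

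In every case the median and quartiles are 0 and the maximum is 1.0. The table signals that at least one subject worsened but does not report how many, or at what grade. The 507 is the planned randomized number, not the Safety population.

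**The case against.** The strongest reply is that coagulation is not ignored. SAP 8.3.2 flags out-of-range values for all laboratory parameters and assigns CTCAE v4 grades by program without limiting either to 8.3.1. Its shift tables name no analytes, so INR could be in them. The descriptive statistics include SD and maximum, so a tail of large rises would not vanish behind the mean. Abnormalities that change management must be reported as adverse events (Protocol 5.7.5 and 8.3.1). An interruption under 6.7.3 meets that test, and the event would be tabulated by worst severity and again under dose hold or modification. All of this stands, and a reader who inferred that coagulation worsening is never tabulated would go further than the text allows.

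It is also fair that Protocol 9.7.2 promises only selected tests, so a reader should not infer a breach of the protocol. For PTT the objection has real force: the protocol names PTT only in the panel, and 6.7.11 monitors bleeding by blood counts and examination, not by coagulation tests.

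What does not stand is that these routes together replace a graded table. None commits to laboratory-based severity grading of INR or PTT. The SAP grades ALT, AST and bilirubin from laboratory data although the same adverse-event route is open to them.

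**Conclusion.** The point holds as a reporting gap of modest size. The SAP's only stated selection of analytes has 0 of the 2 collected coagulation tests, and no other text commits to a graded incidence of INR or PTT worsening from laboratory data.

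The conclusion rests on reading 8.3.1 as the selection behind the graded incidence table; the documents point to no other. Whether the grade-shift, worst-grade and between-arm tables also leave out coagulation is not settled by the text, and that ambiguity is itself a reason to amend it. The case is clear for INR because of 6.7.3. For PTT it rests only on the test being collected. The INR scenario in the working is an assumption and the finding does not depend on it.

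**What to change.** In SAP 8.3.1, add a Coagulation category with INR increased and aPTT prolonged, both graded by CTCAE v4. State that both enter the graded incidence, worst-grade, shift and between-arm difference tables of 8.3.2, using central and local results as for the other analytes. Mark uric acid and ionized calcium as summarized if available, or delete them.

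The cost is two more rows in table programs that already exist; the coagulation data are already collected. The change belongs in a SAP revision or addendum approved before unblinding (SAP 4.8), so that the choice of safety analytes is not made after the results are seen. It changes reporting only, and no dose or clinical rule.
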